### **6.3 Letrozole**

Letrozole at the standard approved dose of 2.5 mg by mouth daily continuous dosing will be prescribed as standard of care for neoadjuvant endocrine therapy through MD Anderson's or the patient's choice of pharmacy. There will be no dose adjustments for letrozole. If the patient is felt to be having unacceptable toxicities due to letrozole, then treatment will be stopped and the patient will come off study. Subsequent treatment will be as per standard of care. Additional details are provided in the package insert in Appendix C.

## 6.4 Concomitant Medications

In general, the use of any concomitant medication or therapies deemed necessary for the care of the patient is permitted with the exception of strong CYP3A inhibitors or inducers.

## 7.0 ADVERSE EVENT MONITORING AND REPORTING

### 7.1 Definition of an Adverse Event

An adverse event is the appearance or worsening of any undesirable sign, symptom, or medical condition occurring after starting the study drug even if the event is not considered to be related to study drug. Medical conditions/diseases present before starting study drug are only considered adverse events if they worsen after starting study drug. Abnormal laboratory values or test results constitute adverse events only if they induce clinical signs or symptoms, are considered clinically significant, or require therapy.

Attribution	Grade 1	Grade 2	Grade 3	Grade 4	Grade 5
Unrelated	Phase I	Phase I	Phase I	Phase I	Phase I
			Phase II	Phase II	Phase II
				Phase III	Phase III
Unlikely	Phase I	Phase I	Phase I	Phase I	Phase I
			Phase II	Phase II	Phase II
				Phase III	Phase III
Possible	Phase I	Phase I	Phase I	Phase I	Phase I
	Phase II	Phase II	Phase II	Phase II	Phase II
		Phase III	Phase III	Phase III	Phase III
Probable	Phase I	Phase I	Phase I	Phase I	Phase I
	Phase II	Phase II	Phase II	Phase II	Phase II
		Phase III	Phase III	Phase III	Phase III
Definitive	Phase I	Phase I	Phase I	Phase I	Phase I
	Phase II	Phase II	Phase II	Phase II	Phase II
		Phase III	Phase III	Phase III	Phase III

### 7.2 Serious Adverse Event (SAE) Reporting

An adverse event or suspected adverse reaction is considered “serious” if, in the view of either the investigator or the sponsor, it results in any of the following outcomes:

- Death
- A life-threatening adverse drug experience – any adverse experience that places the patient, in the view of the initial reporter, at immediate risk of death from the adverse experience as it occurred. It does not include an adverse experience that, had it occurred in a more severe form, might have caused death.
- Inpatient hospitalization or prolongation of existing hospitalization
- A persistent or significant incapacity or substantial disruption of the ability to conduct normal life functions.
- A congenital anomaly/birth defect.
- Hy’s Law

Important medical events that may not result in death, be life-threatening, or require hospitalization may be considered a serious adverse drug experience when, based upon appropriate medical judgment,

they may jeopardize the patient or subject and may require medical or surgical intervention to prevent one of the outcomes listed in this definition. Examples of such medical events include allergic bronchospasm requiring intensive treatment in an emergency room or at home, blood dyscrasias or convulsions that do not result in inpatient hospitalization, or the development of drug dependency or drug abuse (21 CFR 312.32).

- Important medical events as defined above, may also be considered serious adverse events. Any important medical event can and should be reported as an SAE if deemed appropriate by the Principal Investigator or the IND Sponsor, IND Office.
- All events occurring during the conduct of a protocol and meeting the definition of a SAE must be reported to the IRB in accordance with the timeframes and procedures outlined in “The University of Texas M. D. Anderson Cancer Center Institutional Review Board Policy for Investigators on Reporting Serious Unanticipated Adverse Events for Drugs and Devices”. Unless stated otherwise in the protocol, all SAEs, expected or unexpected, must be reported to the IND Office, regardless of attribution (within 5 working days of knowledge of the event).
- **All life-threatening or fatal events**, that are unexpected, and related to the study drug, must have a written report submitted within **24 hours** (next working day) of knowledge of the event to the Safety Project Manager in the IND Office.
- Unless otherwise noted, the electronic SAE application (eSAE) will be utilized for safety reporting to the IND Office and MDACC IRB.
- Serious adverse events will be captured from the time of the first protocol-specific intervention, until 30 days after the last dose of drug, unless the participant withdraws consent. Serious adverse events must be followed until clinical recovery is complete and laboratory tests have returned to baseline, progression of the event has stabilized, or there has been acceptable resolution of the event.
- Additionally, any serious adverse events that occur after the 30 day time period that are related to the study treatment must be reported to the IND Office. This may include the development of a secondary malignancy.

#### **Reporting to FDA:**

- Serious adverse events will be forwarded to FDA by the IND Sponsor (Safety Project Manager IND Office) according to 21 CFR 312.32.

**It is the responsibility of the PI and the research team to ensure serious adverse events are reported according to the Code of Federal Regulations, Good Clinical Practices, the protocol guidelines, the sponsor's guidelines, and Institutional Review Board policy.**

#### **Adverse Event Reporting Period**

The study period during which all AEs and SAEs must be reported begins after informed consent is obtained and starting protocol intervention and ends 30 days following the last administration of study treatment or study discontinuation/termination, whichever is earlier.

After this period, only SAEs that are attributed to prior study treatment will be reported. All AEs, regardless of attribution, will be collected during Phase I and II studies for at least 30 days after last dose of the study drugs.

### 7.3 Recording of Adverse Events

Medical events that may not result in death, be life-threatening, or require hospitalization may be considered a serious adverse drug experience when, based upon appropriate medical judgment, they may jeopardize the patient or subject and may require medical or surgical intervention to prevent one of the outcomes listed in this definition. Examples of such medical events include allergic bronchospasm requiring intensive treatment in an emergency room or at home, blood dyscrasias or convulsions that do not result in inpatient hospitalization, or the development of drug dependency or drug abuse (21 CFR 312.32).

- Important medical events as defined above, may also be considered serious adverse events.
- Any important medical event can and should be reported as an SAE if deemed appropriate by the Principal Investigator. All events occurring during the conduct of a protocol and meeting the definition of a SAE must be reported to the IRB in accordance with the timeframes and procedures outlined in "The University of Texas M. D. Anderson Cancer Center Institutional Review Board Policy for Investigators on Reporting Serious Unanticipated Adverse Events for Drugs and Devices". Unless stated otherwise in the protocol, all SAEs, expected or unexpected, must be reported to the IND Office, regardless of attribution (within 5 working days of knowledge of the event).

Serious adverse events will be captured in the RedCap electronic system from the time of the first protocol specific intervention, until 30 days after the last dose of drug, unless the participant withdraws consent. Serious adverse events must be followed until clinical recovery is complete and laboratory tests have returned to baseline, progression of the event has stabilized, or there has been acceptable resolution of the event. It is the responsibility of the PI and the research team to ensure serious adverse events are reported according to the Code of Federal Regulations, Good Clinical Practices, the protocol guidelines, the sponsor's guidelines, and Institutional Review Board policy.

This study will be performed in compliance with the principles of International Conference on Harmonization (ICH) Good Clinical Practices (GCP) Guideline.

### 7.4 Assessment of Adverse Events

The PI or designee will be responsible for assigning attribution of adverse events to the study agent.

As far as possible, each adverse event should be evaluated using CTCAE V 4.03 criteria to determine:

- The severity grade (mild, moderate, severe) or grade (1-4).
- Its relationship to the study drug(s) (suspected/not suspected).
- Its duration (start and end dates or if continuing at the final exam).
- Action taken (no action taken; study drug dosage adjusted/temporarily interrupted; study drug permanently discontinued due to this adverse event; concomitant medications taken; non-drug therapy given; hospitalization/prolonged hospitalization).
- Whether it constitutes a serious adverse events (SAE).

All AEs and SAEs, whether volunteered by the patient, discovered by study personnel during questioning, or detected through physical examination, laboratory test, or other means, will be reported appropriately.

*Expected AEs are those AEs that are listed or characterized in the Package Insert (PI) or current Investigator's Brochure.*

Unexpected AEs are those not listed in the PI or current Investigator's Brochure or not identified. This includes AEs for which the specificity or severity is not consistent with the description in the PI or Investigator's Brochure. For example, under this definition, hepatic necrosis would be unexpected if the PI or Investigator's Brochure only referred to elevated hepatic enzymes or hepatitis.

The investigator (or physician designee) is responsible for verifying and providing source documentation for all adverse events and assigning the attribution for all adverse events for subjects enrolled.

## **7.5 Communications between the Investigator and Supporting Company Pfizer**

SAEs that occur after completion of the reporting time period as defined above are reportable to Pfizer if the Investigator suspects a causal relationship between the Pfizer product and the SAE. Of note, Pfizer is supporting the study only with provision of palbociclib.

In addition, all SAEs must also be reported to Pfizer within 24 hours, directed to "Pfizer U.S. Clinical Trial Department" using institutional MD Anderson SAE forms to [contact] (See Appendix G in PDOL for Pfizer Reportable Events Fax Form).

## **8.0 STATISTICAL CONSIDERATIONS**

### **Phase I:**

For the phase I portion, a 3+3 design will be used with 3 to 6 patients for each dose escalation cohort (depending on whether a DLT is seen) and 6 patients in the final (RP2D) cohort to assess the primary endpoint of safety and the determination of RP2D. Therefore a minimum of 12 and maximum of 18 patients will be enrolled. This total does not include patients who may need to be replaced if not evaluable for DLT (see Section 3.3).

### **Phase II:**

The Phase II portion will be performed in a different population of patients (early stage) in the pre-operative setting. In order to obtain qualitative information about the dose responsiveness of HCQ when added to letrozole and palbociclib, Part 1 of the Phase II portion will enroll 6 patients at an HCQ dose of 400 mg (if in fact, the RP2D is 600 or 800 mg). Following this, Part 2 will be conducted at the RP2D for HCQ based on the primary endpoint of proportion of patients achieving tumoral CCCA, with the formal statistical plan using a 2-stage Simon optimal design and looking to increase the CCCA rate from 50% with low dose palbociclib + letrozole to 75% after the addition of HCQ. This design requires 11 patients in the first stage and 14 patients in the 2nd stage. It would stop after the 1st stage if no more than 6 patients show CCCA by tumor biopsy after HCQ treatment and declared the treatment as promising if at least 17 out of 25 total evaluable patients exhibit CCCA.

This design has alpha = 4%, 81% power, and a probability of 0.73 of terminating after the 1st stage if the true CCCA rate=50%. For the group of patients at the RP2D, we therefore plan a sample size of 30 patients over 12-15 months, accounting for patient dropout (including those with Ki67 >10% at T1). We have a large eligible patient population and have led national accruals in other multi-center neoadjuvant endocrine trials in post-menopausal women (e.g. ALTERNATE Trial). In addition, recent local experience of conducting window of opportunity trials in this setting have demonstrated the feasibility of accrual at a rate of ~2 patients per month. Thus, we expect to achieve accrual goals.

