### 2.2.3 Phase II Part 2 Primary Objective and Endpoints

To determine whether hydroxychloroquine added to low dose palbociclib and letrozole can increase the proportion of patients whose tumors achieve complete cell cycle arrest (CCCA, defined as the Ki67  $\leq$  2.7%) comparing T2 to T1 as shown in Figure 2, see Section 5.3.4).

The primary endpoint is the increase in percentage of all patients who achieve CCCA with low dose palbociclib and letrozole (at week 2, time T1) compared to that of low dose palbociclib and letrozole with the addition of HCQ (at 5 weeks, day 29, time T2).

A previously conducted trial of neoadjuvant aromatase inhibitor (anastrozole) plus standard dose palbociclib estimated the CCCA probability to be 44% with aromatase inhibitor alone and powered their study to detect a 50% increase of 44% to 66%. A 26% CCCA probability was seen with anastrozole alone and 86% with the addition of standard dose palbociclib. We will aim for a CCCA reference probability of 50% with low-dose palbociclib + letrozole (T1) and a CCCA probability of 75% with the addition of HCQ (see Section 8 for statistical plan and samples size calculations for the Phase II portion).

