### 2.2.4 Phase II Part 2 Secondary Objectives and Endpoints

- To determine the impact of adding hydroxychloroquine to low dose palbociclib and letrozole on breast tumor indices of proliferation, autophagy, senescence, cell cycle control and other intersecting pathways.
- Determine longer term clinical tumor responsiveness and tumor biomarkers indices (for patients who have extended pre-operative therapy, maximum 24 weeks).
- To determine the dose responsiveness of HCQ (400 mg vs. RP2D) on the primary (proportion with CCCA) and secondary clinical/biological endpoints
- To perform exploratory studies on blood-based tumor protein, DNA and RNA biomarkers.
- Obtain additional safety information for the combination of low dose palbociclib, letrozole and hydroxychloroquine.

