#### Phase II Pre-operative “Window” Component:

The “window” component of the trial evaluates the combination of pre-operative palbociclib plus letrozole followed by the addition of hydroxychloroquine (HCQ) for postmenopausal patients with Stage I-III estrogen receptor-positive and HER2-negative breast cancer (Figure 2).

Correlative studies using baseline and follow up breast biopsies and blood work are included in the research plan. The Phase II portion will assess the change in the percentage of all patients who achieve CCCA when adding HCQ to the palbociclib/letrozole combination.

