### **3.4 Phase II Component (Window/Neo-adjuvant Cohorts)**

The “window” component of the trial evaluates the combination of pre-operative palbociclib plus letrozole followed by the addition of hydroxychloroquine (HCQ) for postmenopausal patients with Stage I-III estrogen receptor-positive and HER2-negative breast cancer (Figure 2).

Correlative studies using baseline and follow up breast biopsies and blood work are included in the overall research grant. The Phase II portion will assess the change in the percentage of all patients who achieve CCCA when adding HCQ to the palbociclib/letrozole combination.

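### Part 2's primary endpoint is the rise in CCCA from T1 to T2, but the only decision rule counts CCCA after HCQ against an assumed 50% and never uses the observed T1 rate

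*Combined protocol and SAP*

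**What the plan says.** Section 2.2.3 states: "The primary endpoint is the increase in percentage of all patients who achieve CCCA with low dose palbociclib and letrozole" at T1, compared with the percentage after HCQ is added at T2. Section 3.1 says Phase II will "assess the change in the percentage of all patients who achieve CCCA when adding HCQ", and Section 3.4 repeats it: "The Phase II portion will assess the change in the percentage of all patients who achieve CCCA". Section 3.6 requires interpretable Ki67 at T0, T1 and T2 for evaluability, and sets the baseline Ki67 threshold to help interpret the T1-to-T2 change.

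Section 8.0 describes the plan as "based on the primary endpoint of proportion of patients achieving tumoral CCCA", and Section 2.2.4 also refers to a dose effect "on the primary (proportion with CCCA) and secondary clinical/biological endpoints". The formal design is a Simon two-stage, "looking to increase the CCCA rate from 50% with low dose palbociclib + letrozole to 75% after the addition of HCQ". It stops if 6 or fewer of the first 11 have CCCA on the post-HCQ biopsy, and it "declared the treatment as promising if at least 17 out of 25 total evaluable patients exhibit CCCA".

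On the population, Section 5.2.3.2 takes patients with Ki67 above 10% at T1 off study, and Section 3.7 replaces patients without evaluable Ki67 at all three times. Section 8.0 plans 30 patients, "accounting for patient dropout (including those with Ki67 >10% at T1"). Section 3.8 gives 25 needed plus 5 expected dropouts, and says the total does not count replaced patients.

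**The concern.** The declared endpoint is a change within patients. The rule is a one-sample test of the later value against a constant. It controls error for the statement that T2 CCCA in evaluable patients exceeds 50%, not for the statement that CCCA rose from T1 to T2. Each patient's own comparator is collected by mandatory biopsy and then has no role in the analysis.

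The populations differ as well: all patients in Section 2.2.3, evaluable patients in Section 8.0. Patients removed for T1 Ki67 above 10% cannot have CCCA, which is defined as Ki67 of 2.7% or less. Removing them can only raise the T1 rate among those who remain. The null stays at 50%, and the text does not say which population it describes.

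At stake is the meaning of a promising result. The rationale in Section 1.2 presents this trial's evidence as needed before a more definitive trial.

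**Working it through.** **1. The plan's own figures.** Inputs from Section 8.0: 11 patients in stage 1, stop at 6 or fewer; 14 more in stage 2; promising at 17 or more of 25; rates 50% and 75%. For true T2 rate p,

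P(promising) = Σ over x = 7 to 11 of Bin(x; 11, p) × P(Y ≥ 17 − x), with Y ~ Bin(14, p).

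| Quantity | Stated | Exact |
|---|---|---|
| Early stop at p = 0.50 | 0.73 | 0.726 |
| P(promising) at p = 0.50 | 4% | 4.6% |
| P(promising) at p = 0.75 | 81% | 80.05% |

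The boundaries are the Simon optimal design for one-sided 5% and 80% power. The design arithmetic is not the problem, apart from an alpha that should read about 4.6%.

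**2. What the rule does with T1.** Take a trial that passes stage 1 and ends at 17/25 at T2:

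| T1 CCCA | T2 CCCA | Change (points) | Rule |
|---|---|---|---|
| 12/25 | 17/25 | +20 | promising |
| 17/25 | 17/25 | 0 | promising |
| 19/25 | 17/25 | −8 | promising |

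**3. Effect of the T1 removal.** Let f be the fraction removed for T1 Ki67 above 10%. The documents give no value, so f is assumed. If 50% was meant for all patients, and other dropout is unrelated to CCCA, the T1 rate among evaluable patients is 0.50/(1 − f). Setting T2 equal to T1 (no change) in the formula of step 1:

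| f | Evaluable T1 rate | P(promising) |
|---|---|---|
| 0 | 50.0% | 4.6% |
| 2/30 | 15/28 = 53.6% | 9.1% |
| 3/30 | 15/27 = 55.6% | 12.6% |
| 5/30 | 15/25 = 60.0% | 24.0% |

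**4. How often the rule is met with no net paired gain.** This enumerates T1/T2 pairs exactly with the stage 1 stop, no true change, and an assumed share of patients switching in each direction. The event is 17/25 or more with gains no greater than reversals.

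| Switching each way | T1 = T2 = 50% | 55.6% | 60% |
|---|---|---|---|
| 2% | 2.7% | 7.8% | 15.5% |
| 5% | 1.7% | 5.5% | 11.4% |
| 10% | 1.0% | 3.7% | 8.5% |

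**5. Precision of a paired estimate at n = 25.** A net gain of 6 patients is 6/25 = 24 points. Exact unconditional 95% intervals (score statistic, not adjusted for the stage 1 stop):

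| Gains / reversals | Interval (points) |
|---|---|
| 6 / 0 | 6 to 45 |
| 7 / 1 | 1 to 46 |
| 8 / 2 | −2 to 48 |

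**The case against.** The strongest reply is that there is one question here. Section 2.2.3 itself gives 50% as the T1 reference and 75% as the target with HCQ, then sends the reader to Section 8, which applies those numbers. Testing against a fixed reference is what a single-arm Simon design does, and the wording in Section 2.2.4 is a parenthetical shorthand. This stands as far as it goes: a reader might infer two rival primary endpoints, but the documents support one intended question tested against an assumed comparator. The reply does not supply an analysis of the change that Section 2.2.3 names.

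The 50% also has some context. Section 2.2.3 cites CCCA of 26% with anastrozole alone and 86% with standard-dose palbociclib added. It lies between these, but neither is a rate for the low-dose regimen, and no derivation is given.

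A reader might take 24% as the trial's false-positive rate. The documents do not support that: it needs 50% to refer to all patients, other dropout to be unrelated to CCCA, and all five planned dropouts to be T1 removals. Section 8.0 states the rule for evaluable patients, so 50% may be meant for them. Nor is 5/30 an upper limit on f, since Section 3.8 does not count replaced patients.

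Finally, promising is a screening verdict, and the paired change could be reported without changing the design. That is true, and it is why the remedy is cheap. Without prespecification, though, the definition of success can be chosen after T2 results are known.

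**Conclusion.** The concern holds. The rule in Section 8.0 does not answer the endpoint declared in Section 2.2.3, and it can return promising with no increase or a fall. That much depends on no assumption about rates.

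The size does depend on assumptions. If 50% is right for evaluable patients, the error with no change is 4.6%, and only the mismatch between endpoint and rule remains. If 50% was meant for all patients, the error is 9.1% to 24.0% over the assumed range of 2 to 5 removed per 30. That range is illustrative and not a bound.

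**What to change.** - Keep the Simon rule (6/11, 17/25) as a screen, and state that meeting it shows only that T2 CCCA in evaluable patients exceeds 50%.
- Prespecify, on the same patients, the paired T2-T1 difference in CCCA with an exact 95% interval, noting that it is not adjusted for the stage 1 stop. State that CCCA increased only if the lower limit is above 0.
- Report T1 CCCA for all patients with a T1 biopsy and for evaluable patients, with the number removed for T1 Ki67 above 10%.
- Use one endpoint wording and one population in Sections 2.2.3, 2.2.4, 3.1, 3.4 and 8.0.

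**Cost.** No extra biopsies or patients are needed. The price is imprecision: a 24-point net gain clears 0 with 6 gains and no reversals, or 7 and 1, but not with 8 and 2. The stated power applies only to the T2 screen and should be labelled so.

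Resetting the reference and cut-off to match the evaluable population is a trade-off for the sponsor and not part of this fix. With the 6/11 stop kept, power at the protocol's 75% target would fall from 80% to 55% (at least 19/25) or 38% (at least 20/25).

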### **3.8 Target Accrual**

A total of 54 patients will be enrolled to the study. This includes 2 to 18 patients (up to 6 per dose cohort at 400, 600 and 800 mg of HCQ daily and 6 at the RP2D, but as few as 2 patients in the unlikely event that the first 2 patients experience DLT at the lowest dose of HCQ (400 mg daily) and the study is halted.) in the Phase I metastatic portion, 6 patients for neo-adjuvant Phase II Part 1 and 30 patients for the Phase II Part 2 portion (25 needed for statistical plan and 5 expected to drop out). This does not account for replaced patients (as stated in Sections 3.6 and 3.7).

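### The stated alpha of 4% for the Phase II Part 2 rule is wrong: the exact type I error is 4.6% and the power is 80%, not 81%; the rule itself can stand

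*Combined protocol and SAP*

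**What the plan says.** Section 8.0 (Phase II) describes Part 2 as "with the formal statistical plan using a 2-stage Simon optimal design", aiming to "increase the CCCA rate from 50% with low dose palbociclib + letrozole to 75% after the addition of HCQ". The stage sizes follow: "This design requires 11 patients in the first stage and 14 patients in the 2nd stage". The interim rule is "It would stop after the 1st stage if no more than 6 patients show CCCA by tumor biopsy after HCQ treatment", and the treatment is to be "declared the treatment as promising if at least 17 out of 25 total evaluable patients exhibit CCCA". The operating characteristics are given in one sentence: "This design has alpha = 4%, 81% power, and a probability of 0.73 of terminating after the 1st stage if the true CCCA rate=50"%.

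Two other sections agree with these inputs. Section 2.2.3 names a "CCCA reference probability of 50% with low-dose palbociclib + letrozole (T1) and a CCCA probability of 75% with the addition of HCQ", and Section 3.8 breaks the 30 Part 2 patients down as "25 needed for statistical plan and 5 expected to drop out". The documents state no target alpha or power apart from the 4% and 81%, and no other section gives different error rates.

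**The concern.** The plan fixes every input to the error rates: null rate, alternative rate, both stage sizes and both cut-offs. The three operating characteristics can therefore be computed exactly, and they should agree with the printed values to the last digit shown. One does and two do not. Both discrepancies make the design look slightly better than it is, since alpha is too low and power too high.

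That sentence is the only statement of error rates for the main efficacy decision; Section 3.5 refers to Section 8.0 for that plan. Anyone who takes it at face value would believe that false-positive error is controlled at 4%, which the rule does not achieve.

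**Working it through.** **Inputs**

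- Null and alternative CCCA rates: p0 = 0.50, p1 = 0.75 (Section 8.0 Phase II; Section 2.2.3).
- Stage sizes: n1 = 11, n2 = 14, total 25 (Section 8.0; Section 3.8).
- Stop if X1 ≤ 6; declare promising if X1 + X2 ≥ 17 (Section 8.0).
- Sidedness is not stated; the rule is one-sided by its form.

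**Formulas**

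- Probability of early stopping: P(X1 ≤ 6), with X1 ~ Bin(11, p).
- Probability of declaring the treatment promising: Σ over x = 7 to 11 of P(X1 = x) · P(X2 ≥ 17 − x), with X2 ~ Bin(14, p). At p = 0.50 this is the type I error; at p = 0.75 it is the power.

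**Step 1: the figure that reproduces.** At p = 0.50 the early-stopping probability is 1,486/2,048 = 0.7256. The plan states 0.73, so the null rate and the first-stage boundary are being read as intended.

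**Step 2: type I error at p = 0.50.** Each term is C(11, x) times the number of second-stage outcomes with at least 17 − x responses, and the sum is divided by 2^25 = 33,554,432.

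| x in stage 1 | C(11, x) | Needed in stage 2 | Outcomes out of 2^14 | Product |
|---|---|---|---|---|
| 7 | 330 | ≥10 | 1,471 | 485,430 |
| 8 | 165 | ≥9 | 3,473 | 573,045 |
| 9 | 55 | ≥8 | 6,476 | 356,180 |
| 10 | 11 | ≥7 | 9,908 | 108,988 |
| 11 | 1 | ≥6 | 12,911 | 12,911 |
| Sum | | | | 1,536,554 |

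1,536,554 / 33,554,432 = **0.0458**. The plan states 4%.

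**Step 3: power at p = 0.75.** The same sum gives 0.1276 + 0.2293 + 0.2482 + 0.1533 + 0.0421 = **0.8005**. The plan states 81%.

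A simulation of 2,000,000 trials gave 0.0457 and 0.8003, which agrees with Steps 2 and 3.

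**Step 4: could another reading give 4% and 81%?**

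| Variant | Alpha | Power |
|---|---|---|
| Rule as written (stop ≤6/11, success ≥17/25) | 4.6% | 80.1% |
| Stop ≤5/11, success ≥17/25 | 5.2% | 84.2% |
| Stop ≤7/11, success ≥17/25 | 3.1% | 67.3% |
| Stop ≤6/11, success ≥18/25 | 2.0% | 70.1% |
| Stop ≤6/11, success ≥16/25 | 8.7% | 85.3% |
| Single stage, ≥17/25, no interim stop | 5.4% | 85.1% |

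None of these gives the printed pair. A single-stage normal approximation gives an alpha of 3.6% without continuity correction and 5.5% with it. The rule as written reaches an alpha of 4.0% only if the null rate is 49.35% instead of 50%.

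**Step 5: what the rule was probably built for.** A search over all two-stage designs for 50% against 75%, with alpha ≤ 5% and power ≥ 80%, returns exactly this rule as the one with the smallest expected sample size under the null: 11 + (1 − 0.7256) × 14 = 14.84 patients.

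**The case against.** Three points can be made for leaving the sentence alone, or for saying less about it.

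*The gap is about one unit in the last printed digit.* Truncating 4.58% to a whole percent gives 4%. Truncation does not give 81% from 80.05%, though; either convention gives 80%. The sentence is therefore wrong under any consistent convention. It stands that the gap is small, and the power difference alone would hardly be worth raising.

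*The documents never state limits of 5% and 80%, so keeping the rule rests on inference.* This is fair. If 4% had been a hard ceiling, the rule would breach it. The optimal design for alpha ≤ 4% and power ≥ 80% keeps 6/11 but needs 19 of 28 (alpha 3.6%, power 80.5%); requiring at least 81% power moves it to 20 of 30 (alpha 4.0%, power 82.6%). Against that reading, the sentence reports 4% as a property of the chosen design and not as a limit, and the rule matches the 5%/80% optimum exactly. The inference is strong, but the sponsor can settle it.

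*The 4.6% holds only if 50% is the right null rate among evaluable patients.* Patients with Ki67 above 10% at T1 leave the study (Section 5.2.3.2) and count as dropout (Section 8.0), and all of them are without CCCA at T1. As an assumption, suppose the 50% applies to all patients and 5%, 10% or 16.7% leave this way. The null rate among those who remain is then 0.50/0.95 = 0.526, 0.50/0.90 = 0.556 or 0.50/0.833 = 0.60, and the same rule has a type I error of 7.6%, 12.6% or 24.0%. This is a larger matter, but a separate one: it questions the null rate, not the arithmetic at the stated null rate. Correcting the sentence does not resolve it.

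**Conclusion.** The concern holds. At the plan's own 50% and 75%, the 6/11 and 17/25 rule has a type I error of 4.58% (stated 4%, a gap of 0.58 percentage points) and a power of 80.05% (stated 81%, a gap of 0.95 points). The early-stopping probability of 0.73 is correct. The alpha figure is the substantive error; the power figure is minor.

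This is a reporting correction. True alpha remains below 5% and true power at 80%, so the arithmetic gives no reason to alter the sample size, cut-offs or stopping rule. That conclusion rests on two assumptions: that the intended limits were 5% and 80%, which the rule fits exactly but the documents do not state, and that 50% is the null rate among the evaluable patients. The arithmetic itself needs no assumption beyond the plan's stated inputs.

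**What to change.** Replace the sentence in Section 8.0 (Phase II) with wording such as:

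> For a CCCA rate of 50% under the null and 75% under the alternative, the design has a one-sided type I error of 4.6% and a power of 80%; if the true rate is 50%, the probability of stopping after stage 1 is 0.73.

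State the design limits in the same place (presumably alpha ≤ 5% and power ≥ 80%), so that the choice of rule can be checked. If the sponsor did intend 4% as a ceiling, the rule would have to be re-derived.

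The cost is one sentence, with no change to sample size, cut-offs, stopping rule or conduct.
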